2.1. Summary of Study Design

Study I8F-MC-GPHR (GPHR) is a Phase 2, multicenter, randomized, double-blinded, placebo-controlled study that will investigate the effects of treatment with tirzepatide 5 mg, 10 mg, and 15 mg SC QW compared with placebo on NASH resolution with no worsening of fibrosis in patients with biopsy-proven NASH and fibrosis, with or without T2DM.

Figure GPHR.2.1 illustrates the study design.

[figure not shown]

Figure GPHR.2.1. Illustration of study design for Clinical Protocol I8F-MC-GPHR.

Study GPHR will consist of 3 periods:

- Screening (Visits 1 and 2)
- Treatment (Visits 3 to 14)
 - 4- to 20-week dose escalation (4-week for 5-mg group, 12-week for 10-mg group, 20-week for 15-mg group)
 - 32- to 48-week maintenance (48-week for 5-mg group, 40-week for 10-mg group, 32-week for 15-mg group)
- Safety follow-up (4 weeks post-treatment, through Visit 801)

The maximum total duration of the combined treatment periods is 52 weeks.

Enrichment Strategy

Participants with biopsy-proven NASH will be enrolled into this study. The study population will be enriched for participants who have T2DM, such that 40% to 65% of the total study population will consist of participants with NASH who have also been diagnosed with T2DM. The other 35% to 60% of the study population will consist of participants with NASH who do not have T2DM.

Participant Visit Scheme

Participants with a qualifying liver biopsy performed within 6 months of screening who meet the other required inclusion and exclusion criteria can participate in the study after evaluation of the histology by 2 central pathologists with experience in NASH to confirm presence of NASH and the study-specific histological inclusion criteria. Visit 2 will be omitted for these participants.

Participants without a qualifying liver biopsy will undergo assessments of their CAP and LSM at Visit 1 using TE to determine if they have a high probability of fatty liver disease with fibrosis. Participants meeting prespecified criteria for a high probability of fatty liver disease with fibrosis by TE will undergo a liver biopsy at Visit 2 to assess study eligibility, provided they meet all other required inclusion and exclusion criteria. Liver biopsies will be evaluated by 2 central pathologists with experience in NASH prior to Visit 3 to confirm presence of NASH and study-specific histological inclusion criteria.

2.2. Determination of Sample Size

Sample size selection is guided by the objective of establishing superiority of each tirzepatide dose to placebo relative to the proportion of participants achieving NASH resolution without worsening of fibrosis at 52 weeks from randomization. The evaluation of superiority to placebo will be conducted for each of the 3 tirzepatide doses at 2-sided significance level of 0.05 using a test of 2 proportions. The power is assessed based on the following assumptions:

- the tirzepatide group mean response rate is assumed to be 42.5%
- the placebo group mean response rate is assumed to be 12.5%
- the dropout rate is assumed to be a 20%, and
- 1:1:1:1 randomization.

On the basis of these assumptions, approximately 196 participants will be required to provide at least 80% power to establish superiority of tirzepatide 5-mg, tirzepatide 10-mg, or tirzepatide 15-mg doses to placebo. This results in approximately 40 completers per arm. No adjustment for multiplicity will be performed.

2.3. Method of Assignment to Treatment

Approximately 196 patients who meet all criteria for enrollment will be randomized to one of the study treatment arms at Visit 3. Assignment to treatment arms will be determined by a computer-generated random sequence using an interactive web response system. Patients will be randomized in a 1:1:1:1 ratio to receive 5-mg tirzepatide, 10-mg tirzepatide, 15-mg tirzepatide, or placebo. Patients will be stratified at randomization based on T2DM status (Yes or No) and the region (Japan, US including Mexico, and Europe including Israel).

3. A Priori Statistical Methods

3.1. Population for Analyses

For purposes of analysis, [Table GPHR.3.1](#) defines the following analysis populations/data sets:

Table GPHR.3.1. Analyses Populations/Data Sets

Population/Data Set	Description
Entered population	All participants who sign informed consent
Randomized population	All participants who are randomly assigned to a treatment arm
Modified intent-to-treat (mITT) population	All randomly assigned participants who are exposed to at least 1 dose of study drug. In the event of a treatment error, participants will be analyzed according to the treatment they were randomized.
Efficacy analysis set (EAS)	Data obtained during treatment period from all randomized participants, excluding data after permanent study drug discontinuation. Participants will be analyzed according to the treatment they were randomized.
Exploratory analysis set (EXAS)	Data obtained during treatment period from mITT population participants who stay on study treatment for at least 36 weeks, excluding data after permanent study drug discontinuation.
Full analysis set (FAS)	Data obtained during treatment period from the mITT population, regardless of adherence to study drug.
Safety analysis set (SS)	Data obtained during treatment period plus the safety follow-up period from the mITT population, regardless of adherence to study drug.

3.2. General Considerations

Statistical analysis of this study will be the responsibility of Eli Lilly and Company (Lilly) or its designee. All statistical analyses will be conducted with SAS Version 9.4 or higher unless otherwise stated. Some analyses and summaries described in this analysis plan may not be conducted if not warranted by data (e.g., few events to justify conducting an analysis). Listings of events will be provided in such situations. Additional analyses of the data may be conducted as deemed appropriate without further changes made to the protocol or SAP, even after the primary or final database locks.

Additionally, to avoid potential selection biases, unless stated otherwise, statistical summaries and analyses will be conducted based on randomized study treatment group regardless of the actual treatment received by the patient. Unless otherwise noted, all tests of treatment effects will be conducted at a 2-sided alpha level of 0.05, and the CI will be calculated at 95%, 2-sided. In statistical summaries and analyses, patients will be analyzed as randomized.

For histological, imaging, and TE measurements the last available data during Visit 1 to Visit 3 prior to or within 1 week after the first study drug administration will serve as baseline. For patients who have an eligible historical biopsy within 6 months of Visit 1, the historical biopsy will serve as baseline for histological measures. Unless specified otherwise, the last measurement during Visit 1 to Visit 3 (including unscheduled visits) collected prior to or on the first dose day will serve as baseline. For immunogenicity, data collected up to the first dose time will serve as baseline. For laboratory and ECG, baseline needs to be prior to or within 1 hour after the first dose time. For PROs, data collected at Visit 3, regardless of the timing relative to the first dose, will serve as baseline.

There will be 2 estimands of interest in evaluating the primary and secondary efficacy objectives. The first estimand, the “efficacy” estimand, represents efficacy prior to discontinuation of study drug.

Primary Estimand (efficacy estimand)

The primary clinical question of interest is: What is the treatment difference in NASH resolution without worsening of fibrosis after 52 weeks of treatment assuming all participants who meet the inclusion criteria would have completed the treatment period?

The “efficacy estimand” is described by the following attributes:

- Population: participants who meet the inclusion criteria. Further details can be found in Section 5 of Protocol GPHR.
- Endpoint: NASH resolution without worsening of fibrosis at 52 weeks.
- Treatment condition: the randomized treatment.
- The ICE “permanent discontinuation of study drug” is handled by the hypothetical strategy and the potential outcome of interest is the response in the efficacy measurement if participants had adhered to the randomized treatment. There are no other defined ICES.
- Population-level summary: proportion of patients meet NASH resolution without worsening of fibrosis at Week 52.

Treatment effect of interest is thus defined as the difference in proportion of NASH resolution without worsening of fibrosis at Week 52 between QW LY3298176 (tirzepatide) and placebo. Rationale for “efficacy estimand”: This Phase 2 study aims to study the efficacy of LY3298176 (tirzepatide) under the ideal condition that all participants adhere to the randomized treatment. Data collected after the ICE will be set to missing.

Estimand(s) for Secondary Objectives

The same estimand for the primary objective will be used for the secondary efficacy endpoints for the secondary objectives.

Treatment-regimen estimand

The second estimand, the “treatment-regimen” estimand, represents the efficacy irrespective of adherence to investigational product and availability of the postbaseline biopsy. There are no ICE.

Unless specified otherwise, safety analyses will be conducted using the SS.

The end of study participation for a patient will be the earliest of date of death, date of withdrawal from further participation in the study, or date of the safety follow-up visit (Visit 801). For patients considered to be lost to follow-up, end of study participation will be the date of lost to follow-up reported by the investigator. Patient data included in the database after the last date of study participation (date of death, date of early termination or date of safety follow-up) will be excluded from statistical analyses. A listing of such data may be provided.

Summary statistics for categorical measures (including categorized continuous measures) will include sample size, frequency, and percentages. Summary statistics for continuous measures will include sample size, mean, SD, median, minimum, and maximum. The summary statistics

will be presented by nominal visit. The analysis model to make comparisons among treatment groups relative to continuous measurements assessed over time will be either ANCOVA or an MMRM.

Statistical treatment comparisons will be performed between tirzepatide doses and placebo. The comparison among tirzepatide groups will be performed if deemed necessary.

Statistical summaries and results of statistical analyses will be displayed in the following treatment order: 5-mg tirzepatide, 10-mg tirzepatide, 15-mg tirzepatide, placebo.

Not all analyses described in this SAP will necessarily be included in the CSR. Any analysis described in this SAP and not provided in the CSR would be available upon request.

3.3. Adjustments for Covariates

The study is stratified based on T2DM status (Yes or No) at randomization and the region (Japan, US including Mexico, and Europe including Israel).

For efficacy-related analyses of histological endpoints, region and T2DM status at randomization will be used as covariates. Unless otherwise specified, for efficacy analyses of continuous measurements including non-histological and laboratory biomarkers, corresponding baseline value will be used as an additional covariate to T2DM status and the region.

3.4. Handling of Dropouts or Missing Data

For the analyses of primary and key secondary efficacy endpoints related to histology, data for participants with missing postbaseline liver biopsy will be excluded and not be imputed. A separate analysis for these endpoints may be conducted using FAS, where missing postbaseline biopsies will be imputed based on the method described in Section 3.11.1.3.

Unless specified otherwise, imputation of missing data for exploratory purposes will be limited to primary and key secondary efficacy endpoint analyses.

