3.11. Efficacy Analyses

The assessment of the primary, secondary and exploratory endpoints will be guided by the “efficacy” estimand. Analyses relative to the “efficacy” estimand will be conducted using the EAS without imputation of missing data. For exploratory purposes, and in the event of patients dropping out before Week 36, primary and key secondary efficacy analyses may be repeated using the EXAS guided by the “efficacy” estimand.

For informational purposes, the analysis of primary and key secondary endpoint may be repeated to be guided by the “treatment-regimen” estimand, which represents the efficacy irrespective of adherence to investigational product. Analyses relative to the “treatment-regimen” estimand will be conducted using the FAS. In this case, missing postbaseline measures will be imputed according to Section 3.11.1.3.

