3.11.1.1. The Analysis Relative to the Efficacy Estimand

The analysis related to efficacy estimand will be conducted utilizing the NASH resolution with no worsening of fibrosis (Yes/No) at 52 weeks in the EAS. Logistic regression will be used to evaluate performance of each tirzepatide arm compared to placebo. The test will adjust for stratification factors by including baseline T2DM status (Yes/No) and the region (Japan, US including Mexico, and Europe including Israel).

With the aid of the logistic regression, p-values of the test as well as 2-sided 95% CI of the odds ratio for the proportion of patients achieving NASH resolution with no worsening of fibrosis at 52 weeks between each dose of tirzepatide 5 mg, 10 mg, and 15 mg and placebo will be derived.

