3.11.1.2. The Analysis Relative to the Treatment-Regimen Estimand

The analysis related to treatment-regimen estimand may be conducted utilizing the NASH resolution (Yes/No) with no worsening of fibrosis at 52 weeks in the FAS. The same logistic regression described in Section 3.11.1.3 will be used for the analysis. Multiple imputation of missing NASH resolution status will be conducted before performing the logistic regression (see Section 3.11.1.3).

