3.11.1.3. Methods for Multiple Imputations

For efficacy analyses relative to “treatment-regimen” estimand, the ICEs and the resulting missing values will be handled as follows:

There are no ICE for “treatment-regimen” estimand. If the endpoint biopsy is not collected, data from participants who discontinue, but with non-missing endpoint biopsy from the same treatment arm will be used to impute the missing value (retrieved dropout imputation). In cases where there are not enough retrieved dropouts to provide a reliable imputation model, the imputation of missing data will be done with the jump-to-reference (placebo) imputation approach.

For NASH resolution with no worsening of fibrosis which is a binary endpoint and multiple conditions (see Section 3.11.1) need to be satisfied in addition to no increase in fibrosis score, the imputation will be done for each of the components separately. That is, ballooning score, steatosis score, inflammation score, and fibrosis score will be imputed separately. At the end, the imputed values will determine if the participant satisfies all criteria to have “Yes” for NASH resolution with no worsening of fibrosis or “No” otherwise based on the criteria listed in Section 3.11.1.

The statistical inference over multiple imputation of missing data is guided by methodology proposed by Rubin (1987).

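### The primary estimand asks what would have happened had everyone completed, yet participants without a follow-up biopsy are dropped, with no stated assumption and no required analysis that includes them

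*SAP*

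**What the plan says.** SAP 3.2 poses the primary question as the treatment difference at 52 weeks "assuming all participants who meet the inclusion criteria would have completed the treatment period". Permanent discontinuation of study drug is handled by a hypothetical strategy, and "Data collected after the ICE will be set to missing". The summary measure is explicit: "Treatment effect of interest is thus defined as the difference in proportion of NASH resolution without worsening of fibrosis at Week 52". The secondary endpoints use the same estimand.

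The analysis takes another route. For histology endpoints, SAP 3.4 says "data for participants with missing postbaseline liver biopsy will be excluded and not be imputed", and SAP 3.11 says that efficacy-estimand analyses "will be conducted using the EAS without imputation of missing data". Protocol 9.4.3.1 removes the same participants. The model in SAP 3.11.1.1 is a logistic regression on arm, type 2 diabetes status and region, from which the SAP derives "p-values of the test as well as 2-sided 95% CI of the odds ratio". Protocol 8.1.1 rules out a second biopsy for anyone who stops study drug before Week 36.

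The other planned analyses are these:

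- SAP 3.11.1.2: "The analysis related to treatment-regimen estimand may be conducted". It uses the full analysis set with multiple imputation and addresses a different estimand.
- SAP 5.7: handling of COVID-19 missing data is also worded *may* and borrows that imputation method.
- SAP 3.11.1.4: an optional repeat in the exploratory analysis set, which SAP Table GPHR.3.1 limits to at least 36 weeks on treatment.

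**The concern.** With only arm, diabetes status and region in the model, the complete-case difference in proportions equals the target only if participants without a biopsy would have responded like biopsied participants of the same arm and strata, or if biases happen to cancel. The SAP neither states nor examines this. The odds ratio is less exposed: it is biased mainly when dropout, or its link to outcome, differs between arms.

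The documents give reasons to doubt that dropout is unrelated to arm or outcome. Protocol 4.3 reports gastrointestinal events rising with dose. Protocol 6.6 requires those who cannot tolerate the first escalation to stop, and Protocol 7.1 stops treatment on a diagnosis of cirrhosis.

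The result will be read as the effect had everyone completed, in a study meant to support Phase 3 dose selection (Protocol 2.1). It will describe only participants with a usable biopsy.

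Who has a usable biopsy is itself unsettled. Protocol 8.1.1.3 permits early-termination biopsies after at least 36 weeks on treatment. The efficacy analysis set in Protocol 9.3 needs at least 46 weeks on treatment and a biopsy within 2 weeks of the last dose. The set in SAP Table GPHR.3.1 has neither condition and excludes data after permanent discontinuation. SAP 3.11.1.3 treats such biopsies as retrieved-dropout data: "data from participants who discontinue, but with non-missing endpoint biopsy from the same treatment arm will be used to impute the missing value".

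**Working it through.** **The plan's own figures.** SAP 2.2 assumes 42.5% and 12.5% response, 20% dropout, 1:1:1:1 allocation, 196 randomized and two-sided alpha 0.05.

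- 196 × 0.8 = 156.8, or 39.2 per arm, matching the stated 157 evaluable and about 40 completers per arm.
- The continuity-corrected formula for two proportions at 80% power gives 40 per arm.
- Power at 39 and 40 per arm is 80.8% and 82.1% (Fisher, exact enumeration), or 85.7% and 86.6% (normal approximation).

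The sample size reproduces and is not in question.

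**How many are excluded.** If dropout equals a missing biopsy (an assumption), 0.20 × 196 = 39.2, about 10 of 49 per arm. At 15% it is 29.4 and at 10% it is 19.6.

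**Reference values.**

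- True difference: 42.5 − 12.5 = 30 points.
- True odds ratio: (0.425/0.575)/(0.125/0.875) = 5.17.
- Standard error of the difference at 40 per arm: √(0.425·0.575/40 + 0.125·0.875/40) = 0.094.
- Standard error of the log odds ratio: √(1/17 + 1/23 + 1/5 + 1/35) = 0.575.

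**What one observed result could mean.** Fix the completer rates at 42.5% and 12.5% with 20% missing per arm. The complete-case difference is 30 points whatever the missing participants would have done. The all-completed rate in an arm is 0.8 × completer rate + 0.2 × rate assumed in the missing.

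- Missing respond like completers of their arm: 30.0 points.
- Missing tirzepatide participants at half the completer rate (21.25%), placebo at 12.5%: 38.25 − 12.5 = 25.75.
- All missing at 12.5%: 36.5 − 12.5 = 24.0.
- Missing tirzepatide at 0%, placebo at 12.5%: 34.0 − 12.5 = 21.5.
- Logical bounds: 0.8 × 30 ± 20 = 4 to 44 points.

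**Bias when the truth is 30 points.** In a simulation (2,000,000 per arm), a marker raised the log-odds of response by 0.8 or 1.2 per SD and shifted the log-odds of dropout by −0.7 or +0.7 per SD. These links are assumptions. Cells show the complete-case difference in points and the odds ratio.

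| Dropout, tirzepatide/placebo | Link present in | Poorer responders drop out | Better responders drop out |
|---|---|---|---|
| 20%/20% | tirzepatide only | 32.2–32.9; 5.65–5.81 | 27.0–27.7; 4.56–4.71 |
| 20%/20% | both arms | 31.2–31.7; 5.18–5.22 | 28.7–29.0; 5.27–5.35 |
| 25%/15% | tirzepatide only | 32.8–33.7; 5.80–5.99 | 26.2–27.3; 4.40–4.62 |
| 25%/15% | both arms | 32.1–32.8; 5.43–5.53 | 27.5–28.1; 4.97–5.01 |

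The largest biases on the log odds ratio are ln(4.40/5.17) = −0.16 and ln(5.99/5.17) = +0.15.

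**Why the two measures differ.** Suppose 90% of responders and 77.5% of non-responders are kept in both arms. The observed rate is 0.90p/(0.90p + 0.775(1 − p)). The difference becomes 32.0 points while the odds ratio stays at 5.17.

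**What imputation buys.** A second simulation used 49 per arm, 4,000 trials, 20 imputations, 20% dropout per arm and a link in tirzepatide only. Response and dropout each depended on one measured and one unmeasured factor, and imputation within arm used the measured one.

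- Marker known for all dropouts: bias +2.8 fell to +1.3, and −2.9 to −2.0.
- Marker known for half of them: +2.8 fell to +1.9, and −2.8 to −2.3.
- Root mean squared error fell from 9.8–10.0 to 9.5–9.8.

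Monte Carlo error of each bias is about 0.15 points. The simulation used one binary outcome, not the four separate histology scores.

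**The case against.** **The effect is small.** On a normal approximation, a bias of 2 to 3.8 points lowers 95% coverage only to about 94.5% to 93%, and the worst log odds ratio case gives about 94%. The larger biases need the link in tirzepatide only or unequal dropout. This stands, and it limits the point to a cheap improvement. The smallness is known only under assumed scenarios, though.

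**Complete-case logistic regression is a legitimate, deliberate choice in an exploratory Phase 2 study, and both documents make it.** It is valid if missingness is unrelated to outcome given arm and strata. That also stands. The gap is that the condition is neither stated nor examined.

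**Imputation under missing at random replaces one untestable assumption with another and gains little.** Partly right. It uses baseline and on-treatment information that the planned model ignores, but it does not test dropout driven by unmeasured causes.

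**Other mandatory analyses help.** Body weight and MRI-PDFF are analysed by a repeated-measures model that uses on-treatment data from those who drop out (SAP 3.11.2.1), and SAP 3.7 and 3.9.1 report discontinuation by arm. The concern is therefore confined to histology, which includes the primary endpoint. The discontinuation summaries show who stopped, when and why, but not whether the result depends on it.

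**Dropout is not the same as a missing biopsy.** Correct: those who stop after 36 weeks may be biopsied, so 39 may be too high.

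**The treatment of data after discontinuation differs by estimand, so there is no contradiction.** Largely fair. What remains open is whether a biopsy taken shortly after the last dose counts as on-treatment in the primary analysis.

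**Conclusion.** The concern holds for the primary and histology-based secondary endpoints. The estimand covers all participants as if they had completed. The analysis covers those with a biopsy, and nothing mandatory connects the two. SAP 3.11.1.1 also specifies inference only for the odds ratio, although SAP 3.2 names the difference in proportions as the effect. Making the treatment-regimen analysis mandatory would not close the gap, because it answers a different question.

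The likely bias is about 1 to 4 points in either direction on the difference, and at most about 0.16 on the log odds ratio. Both are below sampling error. Only 42.5%, 12.5%, 20%, 196 and 157 come from the documents; the strength and direction of the dropout links, the unequal dropout and the equation of dropout with missing biopsy are assumptions. This should be fixed, but it does not invalidate the trial.

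**What to change.** 1. In SAP 3.4, 3.11 and 3.11.1.1, state the missing-data assumption behind the efficacy-estimand analysis.
2. Add an analysis, worded *will*, of the primary and histology-based secondary endpoints over all participants in the SAP efficacy analysis set. Multiply impute missing histology by arm under missing at random with a short model: baseline histology, one or two on-treatment measures such as weight or ALT, and MRI-PDFF where available. Then fit the same logistic model. Whether this or the complete-case analysis is primary is the sponsor's choice; report both.
3. Report the difference in proportions with its confidence interval alongside the odds ratio.
4. State whether an early-termination biopsy within 2 weeks of the last dose is on-treatment data, and reconcile the efficacy analysis set in Protocol 9.3 and SAP Table GPHR.3.1 with Protocol 9.4.3.1.
5. Optionally, add a sensitivity analysis that counts discontinuation for diagnosed cirrhosis or death as non-response, labelled as a different estimand.

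No new data are needed, only SAP wording and modest programming. Under Protocol 9.4.1 the sponsor decides whether aligning the protocol needs an amendment or a justification in the SAP. There are three drawbacks. The placebo imputation model would rest on about 5 responders (0.125 × 40). Auxiliary data are scarce for very early stops, since a second MRI after stopping needs at least 16 weeks on treatment (Protocol 8.1.2.2). Bias from unmeasured causes of dropout is only partly removed.
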